4. GENERAL ISSUES FOR DATA ANALYSIS

4.1. General

Descriptive statistics for continuous variables include n (number), mean, standard deviation (SD), median, minimum, and maximum. Minimum and maximum will have the same number of decimal points as the original data. Mean and median will have 1 more decimal point than the original data. Reporting of SD will have 2 more decimal points than the original data.

Descriptive statistics for categorical variables include patient counts and/or counts and percentages. Categories for missing data will be presented, if necessary. Confidence intervals (CIs) of means and/or proportions will be reported as specified. Summaries will be provided overall and by CE-COPD status (CE-COPD: No, CE-COPD: Yes, All) and by COPD severity (Yes: Moderate, Yes: Severe) where appropriate.

4.2. Specification of Baseline Values

4.2.1. Albuterol Use

Baseline albuterol use is defined as the mean number of inhalations per day from day 1 to day 7. If no inhalations were taken during study day 1 through study day 7, the ‘baseline inhalation’ is the first available inhalation after study day 7. For analyses relative to baseline albuterol use, patients who had a CE-COPD during study day 1 through study day 7 will be excluded.

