4.2.3. Inhalational Flow Values

The baseline inspiratory flow values are computed using the set of inhalations taken by the patient during study day 1 through day 7. Among these inhalations, the inhalation with the highest MIF value is considered the ‘baseline inhalation’. The baseline MIF, inhalational volume, inhalation duration, and time to MIF values are those of the identified ‘baseline inhalation’. If no inhalations were taken during study day 1 through study day 7, the ‘baseline inhalation’ is the first available inhalation after study day 7.

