4.2.4. Total Daily Steps

Baseline TDS is the average number of daily steps a patient completes, computed using the daily steps recorded during the first 7 days of study participation (study day 1 through study day 7). The average will be calculated as the sum of the daily TDS divided by the number of days with nonmissing TDS. If no step data are available for study day 1 through study day 7, the ‘baseline TDS’ is the first available TDS after study day 7.

Baseline TDS are computed for those patients in the ankle accelerometry analysis set.

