4.2.5. Sleep Parameters

There are 8 measures of sleep disruption: (i) nighttime average total time in bed, (ii) nighttime average total sleep time, (iii) nighttime average sleep latency time, (iv) nighttime average wakening after sleep onset, (v) total time awake at night, (vi) daytime average minutes asleep, (vii) longest daytime sleep episode and (viii) longest nighttime wake episode. The first 7 sleep parameters are provided via Philips accelerometry and longest nighttime wake episode is derived from the accelerometry data as follows:

The sleep interval data provided via Philips accelerometry includes the activity state ("sleep"/"awake") every 30 seconds during the sleep interval. The number of successive 30 second "awake" states occurring between "sleep" states within the sleep interval is summed to determine the duration of a given "awake" state. The longest nighttime wake episode is the summated "awake" state with the longest duration during the sleep interval.

The baseline value of a given sleep parameter (eg, nighttime average total time in bed) is the average sleep parameter (eg, nighttime average total time in bed), computed using the sleep parameter (eg, nighttime average total time in bed) values captured by accelerometry during study day 1 through day 7. The average will be calculated as the sum of the average sleep parameter divided by the number of days with nonmissing values of the average sleep parameter. If no sleep parameter data are available for study day 1 through study day 7, the 'baseline value of a given sleep parameter' is the first available valid sleep parameter value after study day 7.

Baseline sleep parameters are computed for those patients in the wrist accelerometry analysis set.

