4.6. Handling Withdrawals and Missing Data

Any data that was collected prior a patient's withdrawal from the study will be used for analysis and presented in the data listings.

The following imputation rules will be used;

- If the return date of the last ABS eMDPI device returned is missing the patient's last date of contact if the patient withdrew from the study or the patient's study completion date will be used as the return date (see Section 4.4 and Section 10.2).
- Adverse events or serious adverse events with missing start dates will be considered treatment emergent (see Section 10.4).
- If a patient never used the ABS eMDPI during the study or download of a given ABS eMDPI device was not successful, study day and weekly inhalational flow values will be missing. If download of a given wrist or ankle accelerometer was not successful, TDS and SDI indices will be missing. These missing data will not be imputed.
- In the derivation of Study Day X Inhalation flow values, if there was no albuterol use on Study Day X , then the closest preceding nonmissing Study Day Inhalation is used as the 'Study Day X Inhalation' and the inhalational flow values for Study Day X are assigned accordingly (see Section 7.2.1).
- For patients in the ankle accelerometry analysis set, if no step data are available for study day 1 through study day 7, the 'baseline TDS' is the first available TDS after study day 7 (see Section 4.2.4).
- For patients in the wrist accelerometry analysis set, if no sleep parameter data are available for study day 1 through study day 7, the 'baseline value of a given sleep parameter' is the first available valid sleep parameter value after study day 7 (see Section 4.2.5).
- In the derivation of Study Day X TDS if TDS are missing on Study Day X , then the average of the nonmissing TDS of the 7 days preceding Study Day X is computed and assigned to Study Day X TDS (see Section 7.3.1).
- In the derivation of Study Day X nighttime average sleep latency time if nighttime average sleep latency time is missing on Study Day X , then the average of the nonmissing nighttime average sleep latency time of the 7 days preceding Study Day X is computed and assigned to Study Day X (see Section 7.4.1).

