7.1.1. Albuterol Use Definition

Baseline albuterol use is defined as the mean number of inhalations per day from day 1 to day 7. If no inhalations were taken during study day 1 through study day 7, the ‘baseline inhalation’ is the first available inhalation after study day 7. For analyses relative to baseline albuterol use, patients who had a CE-COPD during study day 1 through study day 7 will be excluded.

Week 1 Patient Albuterol Use: Week 1 patient albuterol use is each patient’s total number of albuterol inhalations taken and the number of days used during the first week (study day 1 through study day 7) of study participation with an indicator of whether or not the most frequent daily usage of albuterol is in 1 of the following 3 categories: (a) 0 to 2 inhalations, (b) 3-6 inhalations and (c) > 6 inhalations. It is presented as WK1:I#iD#dMTN#n, where “i” is the number of albuterol inhalations and “d” is the number of days used in the first 7 days of the study, and “n” is an indicator of whether or not the most frequent daily usage of albuterol falls into one of the 3 categories. If there is a tie in the most frequent daily usage, the category with the highest number of inhalations will be reported. For example, “I28D7MTN2” indicates a total of 28 inhalations were taken, albuterol use was used each of the 7 days and the highest most frequent usage per day falls into category 2 with 3-6 inhalations.

Week 2 Patient Albuterol Use: Week 2 patient albuterol use is each patient’s total number of albuterol inhalations taken and the number of days used during the second week (study day 8 through study day 14) of study participation with an indicator of whether or not the most frequent daily usage of albuterol is in one of the following 3 categories: (a) 0 to 2 inhalations, (b) 3-6 inhalations and (c) > 6 inhalations. It is presented as “WK2:I#iD#dMTN#n”, where “i” is the number of albuterol inhalations and “d” is the number of days used in the second week of study, and “n” is an indicator of whether or not the most frequent daily usage of albuterol is in one of the 3 categories. If there is a tie in the most frequent daily usage, the category with the highest number of inhalations will be reported.

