7.5.2.1. Within Patient CE-COPD Analyses

For each CE-COPD event occurring at least 2 weeks after baseline, device-use measures (albuterol use, inhalational flow [MIF], inhalational volume, and time to MIF) will be summarized for each of 2 weeks of interest: first- 'CE-COPD-adjacent week', the week immediately preceding the onset of CE-COPD symptom (ie, day 1 through 7 preceding the date of the CE-COPD symptom onset), and second – 'CE-COPD-Prior Adjacent week', the week preceding that week (ie, during day 8 through 14 preceding the date of the CE-COPD symptom onset). Summary measures of daily and or weekly use will be compared between the two weeks, as proposed below:

Albuterol use measures:

- total number of inhalations in that week
- the maximal daily number of inhalations in that week
- the mean number of daily inhalations (ie, total number of inhalations divided by number of days with number>0)
- occurrence of a single day's albuterol use exceeding 4 inhalations
- occurrence of a single day's albuterol use exceeding 8 inhalations
- occurrence of a single day's albuterol use exceeding 12 inhalations
- number of days when albuterol use exceeding 4 inhalations
- number of days when albuterol use exceeding 8 inhalations
- number of days when albuterol use exceeding 12 inhalations

To note, in this analysis, no inhalation in any day will be taken as a 0 count.

Inhalation flow values parameters:

- maximal daily MIF during the week
- minimal daily time to MIF within a week
- maximal total daily inhalational volume within a week

To note, if no inhalation was taken at a specific day, flow value parameters will be missing and will not be imputed.

Analysis will be based on all patients CE-COPDs for which there are 14 days (or more) prior to the CE-COPD onset, where patient has been on study and CE-COPD free.

Descriptive statistics of use measures in the 'CE-COPD-adjacent week' and 'CE-COPD-Prior Adjacent week' will be presented.

Continuous measures will be compared between the 2 weeks using paired t-test (and Wilcoxon Signed Ranks test) whereas binary patterns will be compared using Mc-Nemar test.

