20.2. Modified Intent-To-Treat Analysis Set

Statistical Analysis Plan Section	Protocol Section	Protocol Description	Statistical Analysis Plan Change	Rationale
3.2	9.2.2	The modified intent-to-treat (mITT) analysis set is a subset of the ITT analysis set that will include only the patients who used the IMP at any time during the study. This analysis population will be used for endpoint analysis”.	The modified intent-to-treat (mITT) analysis set is a subset of the ITT analysis set that will include patients who used the IMP at any time during the study and patients who did not use the IMP at any time during the study provided these patients complied with study requirements and the ABS eMDPI inhalers were available for data download at the end of the study.	This study is to evaluate the relationship between as-needed usage of ABS eMDPI and CE-COPD/severe CE-COPD. As-needed usage may include no usage if patients' health did not require ABS eMDPI use. Endpoint analyses will be summarized using the ITT analysis set.

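### SAP 4.2.1 and 7.1.1 answer a zero-use first week with a fallback made for flow values, so baseline albuterol use, and the 7.1.2.4 increase triggers built on it, have no single value in those patients

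*SAP*

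**What the plan says.** Section 7.1.1 of the SAP, repeating 4.2.1, states: "Baseline albuterol use is defined as the mean number of inhalations per day from day 1 to day 7". For a week without inhalations, both sections add that the *baseline inhalation* "is the first available inhalation after study day 7. For analyses relative to baseline albuterol use, patients who had a CE-COPD"; the remainder excludes patients with an exacerbation in days 1 to 7.

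The term *baseline inhalation* is defined in 4.2.3, for flow values: "Among these inhalations, the inhalation with the highest MIF value is considered the" baseline inhalation. That section ends with the same fallback.

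The other baselines use a different condition. Section 4.2.4 begins its fallback with "If no step data are available for study day 1 through study day 7", and 4.2.5 with "If no sleep parameter data are available for study day 1 through study day 7". Section 4.6 repeats both among its imputation rules (for steps: "For patients in the ankle accelerometry analysis set, if no step data are available for study day 1 through study day 7") and has no entry for baseline albuterol use.

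Elsewhere the SAP accepts zero as a value. In the within-patient analysis of 7.5.2.1, "no inhalation in any day will be taken as a 0 count". In 20.2, the reason given for changing the mITT set is that "As-needed usage may include no usage".

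Section 7.1.2.4 takes the first single-day rise of 20%, of 2 inhalations and of 4 inhalations over baseline use. The 20% trigger is used again in 7.2.2.1, 7.3.2.1 and 7.4.2.1.

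**The concern.** A flow value cannot exist without an inhalation, so a first-available rule makes sense in 4.2.3. A daily count can exist without one: no inhalations in 7 days gives a mean of 0. The step and sleep fallbacks start when data are absent, and what they substitute is already a daily value. The albuterol fallback starts when use has been observed to be zero, and what it substitutes is a single event.

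Three problems follow.

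- The SAP does not say how one inhalation becomes a number per day, or whether it replaces the computable 0.
- The substitute is taken after the baseline week and may come from the rise that the study is trying to detect.
- A patient who never inhales has no substitute. Such patients belong to the ITT set, on which SAP section 7 runs all endpoint analyses.

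The number of days before the peak when use increased is one of the three albuterol parameters of interest in SAP 1.1, and 7.1.2.4 derives it from baseline use. A baseline that is too high makes the first crossing the same, later or absent, so the lead time is unchanged, shorter or missing.

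**Working it through.** The plan gives no figure to reproduce here. The check finds the smallest whole daily count that meets each trigger under each reading of the fallback.

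**Inputs.** The triggers +2, +4 and 20% come from SAP 7.1.2.4. The baseline b depends on the reading:

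- the day 1 to 7 mean is kept: b = 0/7 = 0;
- one inhalation averaged over the week: b = 1/7 = 0.14;
- one inhalation read as one per day: b = 1;
- the count on the first day of use: b = k (k = 2, 4 and 6 are assumed, for illustration).

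**Convention.** 7.1.2.4 does not say whether a rise must reach or exceed the threshold, and its part on patients without an exacerbation speaks of exceeding it. Both are shown.

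**Formulas.** Under ≥, the count is the smallest integer at or above b + 2, b + 4 or 1.2b. Under >, it is the smallest integer strictly above.

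| Baseline b | +2 / +4 under ≥ | +2 / +4 under > | 20% (same under both) |
|---|---|---|---|
| 0 | 2 / 4 | 3 / 5 | no usable rule |
| 0.14 | 3 / 5 | 3 / 5 | 1 |
| 1 | 3 / 5 | 4 / 6 | 2 |
| k = 2 | 4 / 6 | 5 / 7 | 3 |
| k = 4 | 6 / 8 | 7 / 9 | 5 |
| k = 6 | 8 / 10 | 9 / 11 | 8 |

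In general, the first-use-day reading gives (k + 2) / (k + 4) under ≥ and (k + 3) / (k + 5) under >.

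**Reading the table.**

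- One per day raises both triggers by 1 under either convention; the first-use-day count raises them by k.
- The averaged reading raises them by 1 under ≥ and not at all under >, because 2.14 and 4.14 still round up to 3 and 5.
- At baseline 0, the 20% rise has a zero denominator. Written as 1.2 × 0 = 0, it would be met by every day under ≥ and by any single inhalation under >.

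**Scale.** The example in SAP 7.1.1 has 28 inhalations in week 1, a mean of 28/7 = 4 per day. A patient with no use in week 1 whose first day of use has 4 inhalations gets the same triggers as that patient under the first-use-day reading. That day itself can never count as a rise, since 4 − 4 = 0.

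**Reach.** Three analyses do not use baseline use: the test in 7.1.2.3 (days 1 to 7 against days 8 to 14 before the peak), the paired comparisons in 7.5.2.1 (the two weeks before symptom onset), and the landmark analysis in 7.5.2.2 (fixed counts above 4, 8 and 12). For patients without an exacerbation, the effect on 7.1.2.4 is uncertain: the list there is relative to baseline, but the only numerator written out is days above a fixed 4 inhalations.

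**The case against.** The strongest reply is that the text keeps two terms apart. Baseline albuterol use is the day 1 to 7 mean, which can be computed as 0; the baseline inhalation is a flow-value term and the sentence is a stray duplicate. Section 7.1.2.1 supports this, since it cites the day 1 to 7 average directly. On that reading the +2 and +4 triggers do not move. This reading is available, but it gives the sentence no function in an albuterol-use section and leaves the 20% trigger without a rule. A correction is needed either way.

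Several other points stand. The zero-count statement in 7.5.2.1 is limited to that analysis, and the remark in 20.2 concerns mITT membership; they show how the SAP regards zero use but do not set a baseline rule. The absence of an albuterol-use entry in 4.6 proves little, because the baseline flow fallback is not listed there either. The fallback may have been meant to avoid a zero denominator, but the SAP does not say so, and +2 and +4 have no denominator.

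Setting baseline to 0 also has a price. The prescribed dose is 1 to 2 inhalations, so under ≥ a first routine 2-inhalation dose meets +2, possibly long before the peak.

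A reader might infer that the study's test of rising use before an exacerbation is biased. The documents do not support this: 7.1.2.3 compares two pre-peak weeks and never uses baseline. Nor do they support a claim about the size of the effect on the trial's tables, since they give neither the number of patients with no week-1 use nor those patients' later use.

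**Conclusion.** The point holds as a wrong stated rule with limited reach. For patients with no inhalation on days 1 to 7, baseline albuterol use cannot be programmed in one way. Taken as one per day or as the first-use-day count, the fallback replaces an observed 0 with a post-baseline value and raises the +2 and +4 triggers by 1 or k, under either convention. Averaged over the week, it raises them by 1 only if a rise means at or above the threshold. Left at 0, those triggers are unchanged and the 20% trigger fails in four sections.

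The affected outputs are descriptive. The number of patients is unknown and probably small, because Protocol 4.1 requires current use of a short-acting reliever at entry. The trigger counts rest only on the stated thresholds, the convention chosen and the assumed values of k.

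**What to change.** - **SAP 4.2.1 and 7.1.1.** Set baseline use to 0 when device data for days 1 to 7 were successfully downloaded and show no inhalation. Set it to missing when data from any device in use on those days are unavailable; 4.6 recognises that the download of a given device can fail. Keep the first-available rule for flow values only.
- **SAP 7.1.2.4.** State that an increase means at or above the threshold. Show zero-baseline patients in a separate row, with their number, crossings and lead times.
- **20% trigger** (7.1.2.4, 7.2.2.1, 7.3.2.1, 7.4.2.1). Report it and the summaries that depend on it only for baseline above 0, with the number of patients left out.

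The cost is a short text change in 4.2.1 and 7.1.1, a stated convention and an extra row in 7.1.2.4, and a restriction with a count in the 20% summaries. No new data are needed. The 20% summaries lose some patients, and early +2 crossings on routine doses will appear in the zero-baseline row, which is why that row should be separate.

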7.3.2. Analysis Methods for Total Daily Steps

7.3.2.1. Actual and Change from Baseline in Study Day X Total Daily Steps Prior to the Peak of a CE-COPD

Among patients in the ankle accelerometry cohort who experienced a CE-COPD, summary descriptive statistics of the actual TDS and change from baseline in TDS 1 day (eg, the 24-hour period on the day prior to the date of the CE-COPD symptom peak) and at 3, 5, 7, 10, 14, and 21 days preceding the peak of a CE-COPD, will be presented for all CE-COPDs and by moderate CE-COPDs and severe CE-COPDs.

In this analysis, among patients experiencing more than 1 CE-COPD, the subsequent CE-COPDs will be considered a separate CE-COPD distinct from the first (preceding) CE-COPD provided the patient exhibited at least 1 day of baseline albuterol use after the first (preceding) CE-COPD's date of symptom peak and prior to the subsequent CE-COPD's date of symptom peak. For patients who experience multiple CE-COPDs (eg, 3), for a given number of days preceding a CE-COPD (eg, 7 days), if the (eg, third) CE-COPD overlaps with the time period of the preceding (eg, second) CE-COPD, the CE-COPD (eg, third CE-COPD) will not be included in the analysis.

Among patients in the ankle accelerometry cohort, summary descriptive statistics of the actual TDS and change from baseline in TDS, will be presented for overall, by CE-COPD status, by CE-COPD severity (Yes: severe, moderate; No) and for the first occurrence of a single day increase of 20% from baseline use. For patients who experienced a CE-COPD, the single day increase of 20% from baseline use is defined as the single day increase of 20% from baseline use prior to the exacerbation.

In addition, summary descriptive statistics of the maximum change from baseline in TDS will be presented overall and by CE-COPD status and by CE-COPD severity. For patients who experienced a CE-COPD, the maximum change from baseline in TDS is the maximum change from baseline in TDS during the days prior to the exacerbation.

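### The rule that keeps exacerbations out of the baseline week covers only analyses relative to baseline albuterol use, and no rule keeps out the run-up to events peaking on days 8 to 14

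*SAP*

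**What the plan says.** SAP 4.2.1, repeated in 7.1.1, sets the albuterol baseline: "Baseline albuterol use is defined as the mean number of inhalations per day from day 1 to day 7". It adds one safeguard, limited by its opening words: "For analyses relative to baseline albuterol use", "patients who had a CE-COPD during study day 1 through study day 7 will be excluded".

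The other baselines use the same week without that safeguard:

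- Flow (4.2.3): "The baseline inspiratory flow values are computed using the set of inhalations taken by the patient during study day 1 through day 7". The inhalation with the highest maximal inhalational flow (MIF) supplies all four flow values.
- Total daily steps, TDS (4.2.4): "computed using the daily steps recorded during the first 7 days of study participation", averaged over days with data.
- Sleep (4.2.5): an average over the same 7 days.

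These baselines feed the change-from-baseline summaries at 1 to 21 days before the symptom peak (7.2.2.1, 7.3.2.1, 7.4.2.1) and the weekly ones for weeks 1 to 12 (7.2.2.2, 7.3.2.2, 7.4.2.2). The albuterol baseline feeds the +20%, +2 and +4 inhalation thresholds in 7.1.2.4. None of these sections sets a minimum study day for the event. SAP 8 plans no sensitivity analysis.

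**The concern.** The SAP accepts for albuterol that a week containing an exacerbation is not a usable baseline. The same reasoning applies to steps, sleep and flow. Without the exclusion, a patient who exacerbates in week 1 carries an exacerbation-week reference through every later summary in the CE-COPD: Yes group.

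The second gap follows from the SAP's own hypothesis. Section 7.1.2.3 expects use to rise in the 7 days before the peak. For a day-8 peak those 7 days are exactly the baseline week, and for peaks on days 9 to 14 they overlap it in part. The change being looked for is then partly subtracted from itself. The number of days before the peak when albuterol use increased is a named parameter of interest (SAP 1.1), so a missed threshold crossing distorts it directly.

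The albuterol exclusion also does not say which date places an event in days 1 to 7. Elsewhere the SAP uses symptom peak (7.5.1), symptom onset (7.5.2.1) and the adverse-event start date (7.1.2.2).

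**Working it through.** **Inputs.** 360 evaluable of 400 enrolled, rates of 1.05 and 1.14 per year (midpoint 1.095), 91 expected events with range 73 to 110 (SAP 2.3); baseline on days 1 to 7 (4.2.1, 4.2.3 to 4.2.5); 7-day run-up (7.1.2.3); accelerometer subsets of 100 each (1.1). Assumed, because the documents give no figure: events spread evenly over 84 study days, and a change over the run-up that is either linear or constant.

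**1. The plan's own figure.** 360 × 1.095 × 12/52 = 90.97 events. The Poisson 95% range is 73 to 110, and the probability of at least 70 events is 0.990. This reproduces SAP 2.3, which gives no figure for the baseline rule.

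**2. Events affected, albuterol.** Days 1 to 7: 91 × 7/84 = 7.6 events, already excluded, leaving 83.4. Peaks on days 8 to 14: another 7.6, or 7/77 = 9.1% of those retained.

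**3. Share of the change absorbed by an averaged baseline.** Linear: the day d days before the peak carries (8 − d)/7 of the change seen on the day before the peak. Constant: each of the 7 days carries all of it. Averaging over study days 1 to 7:

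| Peak day | Linear | Constant |
|---|---|---|
| 8 | 28/49 = 57% | 7/7 = 100% |
| 9 | 21/49 = 43% | 6/7 = 86% |
| 10 | 15/49 = 31% | 5/7 = 71% |
| 11 | 10/49 = 20% | 4/7 = 57% |
| 12 | 6/49 = 12% | 3/7 = 43% |
| 13 | 3/49 = 6% | 2/7 = 29% |
| 14 | 1/49 = 2% | 1/7 = 14% |
| Mean | 24.5% | 57.1% |

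**4. Averaged over all retained albuterol events.** Linear: 9.1% × 24.5% = 2.2%. Constant: 9.1% × 57.1% = 5.2%.

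**5. Thresholds, illustration.** Assume steady use of 4 a day and a constant rise of 2. With a day-11 peak, days 4 to 7 are raised, so baseline is (3 × 4 + 4 × 6)/7 = 5.14. The recorded change is 6 − 5.14 = 0.86, or 17%. A true 50% rise misses both +20% and +2 at these expected values.

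**6. Steps and sleep.** Expected events per subset: 91 × 100/400 = 22.75. Peaks on days 1 to 14: 22.75 × 14/84 = 3.8, half of them on days 1 to 7. With no exclusion and a constant change, peaks on days 2 to 14 are affected: 13 of the 83 peak days that have a prior study day, 15.7%. The average loss is (21/7 + 28/7)/83 = 8.4% if values return to normal on the peak day, and (6 + 4)/83 = 12.0% if they stay abnormal for 7 more days.

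**7. Flow.** Step 3 does not carry over, because baseline MIF is a weekly maximum. If MIF falls linearly, the least affected baseline day carries 1/7 (14%) of the fall for a day-8 peak and none for peaks on days 9 to 14. With a constant fall of one within-patient SD and two inhalations a day (simulation, independent normal values), the loss is the whole fall at day 8, 35% at day 11 and 7% at day 14. A second bias runs the other way. Baseline is the best of a week and Study Day X the best of one day (7.2.1), so a fall of about 1.0 to 1.1 SD appears with no true change at 2 to 4 inhalations a day. In the same simulation a day-8 peak records a fall of about 1.14 SD whether the true fall is 1 SD (overstated) or 2 SD (understated).

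**8. Longer run-ups.** Constant rise, albuterol: a 14-day run-up affects 18.2% of retained events with 14.3% average loss; a 21-day run-up affects 27.3% with 23.4%. These lengths appear in the SAP as look-back days, not as its hypothesis.

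**The case against.** The strongest reply is that little depends on this. The affected summaries are descriptive, and the study is exploratory. The tests of the pre-event rise, in 7.1.2.3 and 7.5.2.1, compare days 1 to 7 with days 8 to 14 before the event and never use the baseline week. That stands. A reader might infer that the test of the study hypothesis is biased by the baseline rule; the documents do not support it.

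Other limits also stand:

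- The 57% for a day-8 peak under a linear rise is the worst day, not a typical loss, and it does not apply to MIF.
- For albuterol, the exacerbation itself is already excluded. It could enter only if the rule is read by peak date (an assumed 2 to 4 day lag from onset to peak lets through 2 × 91/84 to 4 × 91/84, about 2 to 4 events) or if the event began before day 1.
- The summaries at the first 20% increase in 7.2.2.1, 7.3.2.1 and 7.4.2.1 are keyed to baseline use. If that means albuterol use, the existing exclusion plausibly reaches them.
- One might read 7.5.2.1, which requires 14 event-free days, as a baseline safeguard that the other sections omit. It is anchored to onset and secures two comparison weeks; it does not protect a baseline.

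None of this explains why flow, steps and sleep lack the exclusion that albuterol has. Even timing may also be too favourable. The entry criteria do not exclude a recent exacerbation, and the reason recorded in Protocol 16.3 for deleting such a criterion is that risk is highest in the following 30 days.

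**Conclusion.** The point holds as an inconsistency with a modest effect. The flow, step and sleep baselines can be exacerbation-week values. For peaks on days 8 to 14 the hypothesised run-up sits partly or wholly in the baseline week. Change from baseline and threshold crossings for albuterol, and change from baseline for steps and sleep, are attenuated.

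Over all retained albuterol events the attenuation averages about 2% to 5%. It is larger for the individual early events, and for steps and sleep about 4 of about 23 events per subset are exposed. These sizes rest on even event timing, a 7-day run-up and the two assumed shapes; early clustering or a longer run-up would raise them.

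It would be too strong to say that change from baseline is understated for every measure. For MIF the contamination is small on average, and the week's-best against day's-best comparison pushes the other way, so the net direction is uncertain.

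**What to change.** 1. In SAP 4.2.3, 4.2.4 and 4.2.5, apply the day 1 to 7 exclusion already used in 4.2.1.
2. In all four sections, state whether onset or peak date places an event in days 1 to 7.
3. In the baseline-dependent pre-event and threshold summaries (7.1.2.4, 7.2.2.1, 7.3.2.1, 7.4.2.1), exclude events peaking before day 15 or report them separately. The day-15 cut follows from the 7-day run-up in 7.1.2.3.

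The change is to SAP wording only. If early events are excluded, about 9% of otherwise eligible events (7/77) leave the albuterol summaries and about 17% (14/84) leave the flow, step and sleep summaries. About 91 × 70/84 = 75.8 of 91 events remain, before allowing for the smaller accelerometer subsets. Reporting the days 8 to 14 events separately keeps them in view.
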